9.2. Stratified Randomization – See section 4.4

9.3. Outcome Measures and Statistical Hypotheses, as outlined in the Specific Aims

Specific Aim 1: Characterize the effects of acupuncture on QST (cold and vibration sensation thresholds) and nerve conduction parameters in the Median and Ulnar nerves.

Hypothesis: Acupuncture will cause decrease in cold and vibration detection thresholds (improve sensation) in the underlying nerve sensory distribution only. Acupuncture will cause NCS changes, characteristic of improved nerve function.

The outcomes generated in this aim will be the baseline and post-acupuncture values of CDT and VDT from Week 1 and Week 2, as well as baseline and post-acupuncture nerve conduction study data from both weeks, consisting of: distal motor/sensory latencies, CMAP and SNAP amplitudes, CMAP area and duration, nerve conduction velocities.

Specific Aim 2: Compare the effects of acupuncture on a diseased nerve (Median) to those of a healthy nerve (Ulnar), using QST (cold and vibration sensation thresholds) and NCS parameters.

Hypothesis: There will be greater change in cold and vibration detection thresholds and NCS parameters in the median nerve compared to the ulnar, due to the lower functional baseline of the median nerve.

The outcomes generated in this aim consist of statistical comparison of acupuncture-induced CDT, VDT and NCS changes in the Median nerve to those in the Ulnar nerve. The Post- minus Pre-acupuncture differences will be compared for the Median and Ulnar nerves in pooled data from all 3 groups, using independent sample t-testing.

Specific Aim 3: Compare the effects of manual acupuncture to those of low-frequency and high-frequency electroacupuncture.

Hypothesis: High-frequency electroacupuncture will have greater effect on NCS, QST followed by low-frequency electroacupuncture and manual acupuncture, in accordance to traditional practices. Acupuncture-induced changes in CDT, DVT and NCS parameters will be compared among the 3 groups (Post- minus Pre- changes), using ANOVA.

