Specific Aim 2: For the current study, the Ulnar nerve is serving as a healthy control to allow for comparison to the diseased Median nerve post-intervention. Historic studies measuring the local, direct effect of acupuncture on a healthy nerve or studies comparing the local effects of acupuncture on a healthy versus a diseased nerve are not available. With respect to our Specific Aim 2 hypothesis, the Ulnar nerve is serving as a disease-free control condition, wherein acupuncture-dependent change in QST and NCS in the Ulnar nerve is anticipated to be largely negligible as the nerve is already functioning at optimal physiologic parameters. Due to this expectation of negligible treatment effect in the Ulnar nerve, the proposed sample size from Specific Aim 1 (20 subjects per acupuncture modality) is expected to be sufficient for these comparisons within each type of acupuncture. Further, we plan to carry out the Median/Ulnar nerve comparisons separately for each of the 3 intervention modalities. The use of both Median and Ulnar nerves lets the treatment as well as control conditions of interest come from the same subjects, allowing them to serve as their own controls. However, this repetition design warrants the use of mixed-model analysis so the random-effects portion can account for the intra-subject serial correlation expected with repeated measurements.

Specific Aim 3: With regards to the proper sample size for comparison among the 3 types of acupuncture – we based the sample size calculation for each study arm in part on the effect sizes observed by Lang et al (42), who enrolled 24 healthy subjects in 6 groups involving a cross over between manual, low-frequency and high-frequency acupuncture and were able to observe significant differences in QST (CDT) between the 3 acupuncture modalities, $p=0.0034$. In our current study, the cross-over design is based on the comparisons of Median and Ulnar nerves; however, the individual methods of acupuncture will be populated by different cohorts. For this reason, the random-effects blocking of our mixed- models will have the nerve dependence

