9.4. Statistical Analysis Plan

Primary statistical analysis for all 3 Specific Aims will use linear mixed-effect models to evaluate the effects of treatment group and intervened nerve location on the outcome measures described above. A mixed-model design will be used to create an intention-to-treat framework

and allow for any missing data. Principal assessment will be on the change in outcomes resulting from acupuncture intervention, calculated as the difference in outcomes before and after treatment. These outcomes will include CDT and VDT, distal motor/sensory latencies, CMAP and SNAP amplitudes, CMAP area and duration, nerve conduction velocities (Specific Aim 1). Acupuncture characterization will be carried out first in the Median and Ulnar nerves of the arm (Specific Aims 1, 2). In both Median and Ulnar nerve interventions, group will be a three level factor based on the type of acupuncture - MA, LF-EA and HF-EA (Specific Aim 3).

Specific Aims 1 and 2:

As a principal independent variable, location of the intervention will be a four-level factor encompassing the possible combinations of treated and evaluated nerves. For Specific Aims 1 and 2, these levels will be: MM – Median treated and tested, MU – Median treated and Ulnar tested, UM – Ulnar treated and Median tested, and UU – Ulnar treated and tested. A time variable (Week 1, Week 2) will also be included to test for any effects due to order of the treated nerves. Additional covariates known to be associated with QST and NCS outcomes such as age and gender will be corrected for as well. Secondary analysis will include treatment evaluations of outcomes within each location of intervention and additional contrasts between the four time points (pre and post treatment for both Week 1 and Week 2). Persistence of the acupuncture effects will specifically be assessed by comparing changes in outcomes after the first treatment but before the second session.

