Another way to characterize the wash-out effect of acupuncture is to compare baseline data from Week 1 and Week 2. We will perform an exploratory analysis to assess for an interaction between location and time, in a mixed linear model. We will incorporate nerve location, evaluation time and the location-time interaction to check for dependencies between Week 1 and Week 2. As stated, the dependent outcomes of all models are the change in QST and NCS from baseline to post-acupuncture. This will allow for a full assessment of washout and carry-over effects with respect both to the nerve location (healthy Ulnar vs diseased Median), time (Week 1 vs Week 2) as well as the order of nerve assessment (the interaction). However, with the repeated nerve measures, it will still be necessary to utilize a mixed-model approach so that the random-effects blocking (nerve location dependent on subject) will allow for the intra-subject serial correlation. For the final model, although exploration of the wash-out effect will be critical, it will pose to be impractical to keep all these covariates in the final model. Only significant time-dependent interactions will be included since the model would otherwise suffer from overfitting due to too many covariates and the limited sample size.

Specific Aim 2: Following completion of Specific Aim 1, we expect to see significant acupuncture effect on the Median nerve (within each acupuncture group). In our proposed mixed linear model for Specific Aims 1 and 2 this would represent MM on the level of each individual group (MA, LF-EA, HF-EA). Conversely, we do not expect to observe a significant effect of acupuncture on the healthy Ulnar nerve as it is already functioning at optimal physiologic level. This would be the UU at the level of each individual group and corresponds to a clinical control. We will conduct direct contrasts between MM and UU as part of the mixed linear model with nerve location, time dependencies and random-effects grouping following the same design as in Specific Aim 1.

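### Aim 2: section 9.3 names a pooled independent-samples t-test for own-control data, against the within-subject contrast of 9.1 and 9.4, and 9.1 calls 20 per modality sufficient without stating a correlation

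*Combined protocol and SAP*

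**What the plan says.** Three sections describe the Aim 2 comparison of acupuncture-induced change in the median and ulnar nerves.

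- **Section 9.3 (Specific Aim 2):** the changes "will be compared for the Median and Ulnar nerves in pooled data from all 3 groups, using independent sample t-testing". The sentence does not say whether this test is primary, secondary or supportive.
- **Section 9.1 (Specific Aim 2):** treatment and control conditions "come from the same subjects, allowing them to serve as their own controls", and a mixed model is wanted "so the random-effects portion can account for the intra-subject serial correlation expected with repeated measurements". On level, "we plan to carry out the Median/Ulnar nerve comparisons separately for each of the 3 intervention modalities". The same paragraph carries the Aim 1 sample size of 20 per modality over to Aim 2, on the ground that little change is expected in the healthy ulnar nerve.
- **Section 9.4:** "Primary statistical analysis for all 3 Specific Aims will use linear mixed-effect models". For Aim 2, "We will conduct direct contrasts between MM and UU as part of the mixed linear model". MM is described within each modality, and so is UU: "This would be the UU at the level of each individual group". The sentence that specifies the contrast does not repeat the modality level. The Aim 3 paragraph declines a single model holding both the four-level location factor and modality, but no sentence says the location model will be fitted within each modality.

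No section gives a correlation between median and ulnar changes, or a variance for their difference.

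**The concern.** The sections differ on the test (independent or within-subject) and on the level (60 subjects pooled or 20 per modality). An independent-samples t-test treats paired data as unrelated, so its standard error is wrong unless the correlation is zero, and it gives up the own-control design that 9.1 relies on. The level matters as much: 60 pairs and 20 pairs give very different power, and section 9.4 plans no multiplicity adjustment, so an unranked choice should not be left open.

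The sample-size statement is a second matter. If the ulnar mean change is zero, the expected MM-UU difference equals the Aim 1 effect. The ulnar measurements still vary, and that variance enters the difference.

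**Working it through.** **Inputs from 9.1.** CDT effect 0.35 °C with 0.696 labelled as the variance of change; NCV effect 3.7 m/s with variance 33.2 (SD 5.76); 20 per arm, alpha 0.05, 80% power; 60 completers.

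**Assumed here.** Two-sided tests; ρ = 0, 0.3 and 0.5; ulnar mean change zero, as 9.1 expects; equal variances in the two nerves. Section 9.1 makes the variance assumption for QST. For NCV it is my extension, and 33.2 comes from a between-patient CTS cohort, not from change scores.

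**Step 1: the plan's own figure.** One-sample pre/post formula: n = (1.960 + 0.842)² σ²/δ² = 7.85 σ²/δ².

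- NCV: 7.85 × 33.2/3.7² = 19.04, so 20. The plan's figure reproduces; noncentral-t power at n = 20 is 78%.
- CDT, 0.696 as a variance: 7.85 × 0.696/0.35² = 44.6, so 45. Power at n = 20 is 43%.
- CDT, 0.696 as an SD: the SDs 0.9 and 0.4 quoted in 9.1 pool to √((0.81 + 0.16)/2) = 0.696, so this reading is plausible. Then 7.85 × 0.696²/0.35² = 31.04, so 32. Power at n = 20 is 57%.

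The Aim 1 benchmarks at n = 20 are therefore 78% for NCV and 43% or 57% for CDT.

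**Step 2: the 9.3 t-test, MM against UU in 60 pairs.** It uses the standard error σ√(2/n); the true one is σ√(2(1−ρ)/n). The ratio 1/√(1−ρ) is 1.00, 1.20 and 1.41 at ρ = 0, 0.3 and 0.5. True alpha is about 2[1 − Φ(1.96/√(1−ρ))]:

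- ρ = 0.3: 2[1 − Φ(2.34)] = 1.9%; simulation 2.0%.
- ρ = 0.5: 2[1 − Φ(2.77)] = 0.6%; simulation 0.6%.
- ρ = 0: 5.0%, no penalty.
- ρ = −0.3, as an illustration: 2[1 − Φ(1.72)], about 8.6%.

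Power, independent against paired, 60 pairs:

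| | ρ = 0.3 | ρ = 0.5 |
|---|---|---|
| CDT, 0.696 as variance | 65 vs 77% | 67 vs 89% |
| CDT, 0.696 as SD | 82 vs 90% | 86 vs 97% |
| NCV | 97 vs 98.5% | 98 vs 99.8% |

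**Step 3: MM-UU within one modality, n = 20.** The SD of the difference is σ√(2(1−ρ)), which equals σ only at ρ = 0.5. For NCV it is 8.15, 6.82 and 5.76 m/s at ρ = 0, 0.3 and 0.5. Power by noncentral t, 19 df:

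| | ρ = 0 | ρ = 0.3 | ρ = 0.5 | Aim 1 benchmark |
|---|---|---|---|---|
| NCV | 49% | 63% | 78% | 78% |
| CDT, 0.696 as variance | 24% | 33% | 43% | 43% |
| CDT, 0.696 as SD | 33% | 44% | 57% | 57% |

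Eighty percent at n = 20 needs a standardised difference of 0.6604. For NCV, 3.7/√33.2 = 0.6421, so the required ρ is 1 − (0.6421/0.6604)²/2 = 0.53. The level also matters: at ρ = 0.5 and with 0.696 as a variance, the paired CDT contrast has 89% power pooled and 43% by modality.

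**Step 4: the covariance in the 9.4 model.** Each completer gives four changes. MM and MU share a session, MM and UM share a tested nerve, and MM and UU share neither. Suppose correlations of 0.5, 0.3 and 0.1 respectively. A simple random intercept imposes one common value, their average: (0.5 + 0.3 + 0.1)/3 = 0.3. The model then takes Var(MM−UU) as 2σ²(1 − 0.3) = 1.4σ², when it is 2σ²(1 − 0.1) = 1.8σ². The standard error is too small by √(1.4/1.8) = 0.88, and alpha is about 2[1 − Φ(1.96 × 0.882)] = 8.4%. Simulation gives about 8.3% at n = 20 and at n = 60; a paired t-test holds about 5%.

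**The case against.** The strongest reply is that the document ranks its own analyses. Section 9.4 makes the mixed model primary for all three aims and specifies the MM-UU contrast, and 9.1 explains why. On that view the t-test is a leftover sentence in a section on outcomes, in a pilot whose analyses are declared exploratory. Most of this stands. A reader might infer that the primary Aim 2 analysis ignores the pairing; the documents do not support that. What remains is that 9.3 gives its test no rank, and 9.4 does not settle the level.

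Second, every penalty in step 2 depends on an assumed ρ. MM and UU come from different nerves in different weeks, so ρ may be low. That stands, but it cuts both ways: a low ρ shrinks the t-test problem and enlarges the sample-size problem. The coefficients above 0.9 in section 2.6 concern the reproducibility and validation of the QST system, not the correlation of median and ulnar changes.

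Third, 9.1 does offer an effect-size anchor: a matched-location median-against-ulnar CDT difference of 0.337 °C in three pilot subjects. It supports the size of the effect but gives no variance for the difference.

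Fourth, one might read 9.3 as pooling all four changes, including those in the untreated nerve. Section 3 (healthy versus diseased nerve) and 9.4 point to MM and UU, so that reading is strained and I do not rely on it.

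**Conclusion.** The inconsistency is real and should be fixed; it does not invalidate the plan. The 9.3 test is wrong for own-control data: conservative under positive correlation, harmless at zero and anticonservative under negative correlation. Its cost in power at 60 pairs is material for CDT and small for NCV.

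The sufficiency statement in 9.1 does not follow from the reason given. With equal variances, Aim 1 power carries over only if ρ is at least 0.5. For NCV the loss at ρ = 0.3 is 15 points (78 to 63%). For CDT it is 10 points (43 to 33%) or 13 points (57 to 44%), depending on how 0.696 is read. A reader might take the whole CDT shortfall from 80% as an Aim 2 defect. It is not: most of it is already present in Aim 1 and is a separate issue.

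Nor should one conclude that the 9.4 model is sound, or unsound, as written. Its covariance structure is not fixed. A simple random intercept can understate the MM-UU standard error, and the 8.3% figure holds only under the correlations assumed in step 4.

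**What to change.** 1. In 9.3, replace the independent-samples t-test with the within-subject MM-UU contrast of 9.4. The mixed model also keeps subjects who leave after Week 1, whose data sections 5.3 and 8 promise to include.
2. In 9.4, specify a covariance that does not force equal correlations among the four changes: for example unstructured, or subject plus session and nerve effects. Report a paired t-test of MM-UU in completers as a check.
3. Before unblinding, name either the by-modality or the pooled contrast as the Aim 2 test, with the other secondary. If by modality, say that the location model is fitted within each modality. The choice is the sponsor's.
4. In 9.1, replace the statement that 20 per modality is sufficient with the power of the MM-UU contrast at the chosen level over a stated range of ρ, after clarifying whether 0.696 is a variance or an SD.

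The cost is wording in 9.1, 9.3 and 9.4, a short power table, and a less favourable stated power if the by-modality test is chosen. No new patients or data are needed.

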9.4. Statistical Analysis Plan

Primary statistical analysis for all 3 Specific Aims will use linear mixed-effect models to evaluate the effects of treatment group and intervened nerve location on the outcome measures described above. A mixed-model design will be used to create an intention-to-treat framework

and allow for any missing data. Principal assessment will be on the change in outcomes resulting from acupuncture intervention, calculated as the difference in outcomes before and after treatment. These outcomes will include CDT and VDT, distal motor/sensory latencies, CMAP and SNAP amplitudes, CMAP area and duration, nerve conduction velocities (Specific Aim 1). Acupuncture characterization will be carried out first in the Median and Ulnar nerves of the arm (Specific Aims 1, 2). In both Median and Ulnar nerve interventions, group will be a three level factor based on the type of acupuncture - MA, LF-EA and HF-EA (Specific Aim 3).

Specific Aims 1 and 2:

As a principal independent variable, location of the intervention will be a four-level factor encompassing the possible combinations of treated and evaluated nerves. For Specific Aims 1 and 2, these levels will be: MM – Median treated and tested, MU – Median treated and Ulnar tested, UM – Ulnar treated and Median tested, and UU – Ulnar treated and tested. A time variable (Week 1, Week 2) will also be included to test for any effects due to order of the treated nerves. Additional covariates known to be associated with QST and NCS outcomes such as age and gender will be corrected for as well. Secondary analysis will include treatment evaluations of outcomes within each location of intervention and additional contrasts between the four time points (pre and post treatment for both Week 1 and Week 2). Persistence of the acupuncture effects will specifically be assessed by comparing changes in outcomes after the first treatment but before the second session.

Another way to characterize the wash-out effect of acupuncture is to compare baseline data from Week 1 and Week 2. We will perform an exploratory analysis to assess for an interaction between location and time, in a mixed linear model. We will incorporate nerve location, evaluation time and the location-time interaction to check for dependencies between Week 1 and Week 2. As stated, the dependent outcomes of all models are the change in QST and NCS from baseline to post-acupuncture. This will allow for a full assessment of washout and carry-over effects with respect both to the nerve location (healthy Ulnar vs diseased Median), time (Week 1 vs Week 2) as well as the order of nerve assessment (the interaction). However, with the repeated nerve measures, it will still be necessary to utilize a mixed-model approach so that the random-effects blocking (nerve location dependent on subject) will allow for the intra-subject serial correlation. For the final model, although exploration of the wash-out effect will be critical, it will pose to be impractical to keep all these covariates in the final model. Only significant time-dependent interactions will be included since the model would otherwise suffer from overfitting due to too many covariates and the limited sample size.

Specific Aim 2: Following completion of Specific Aim 1, we expect to see significant acupuncture effect on the Median nerve (within each acupuncture group). In our proposed mixed linear model for Specific Aims 1 and 2 this would represent MM on the level of each individual group (MA, LF-EA, HF-EA). Conversely, we do not expect to observe a significant effect of acupuncture on the healthy Ulnar nerve as it is already functioning at optimal physiologic level. This would be the UU at the level of each individual group and corresponds to a clinical control. We will conduct direct contrasts between MM and UU as part of the mixed linear model with nerve location, time dependencies and random-effects grouping following the same design as in Specific Aim 1.

Specific Aim 3: We will revise the linear mixed model and focus on the MM factor from Specific Aims 1 and 2 (Median nerve treated and tested). In this revised model we will incorporate acupuncture modality as a 3-factor covariate (MA, LF-EA, HF-EA). Incorporating both the 4-factor sets of nerve intervention/assessment combinations and the 3-factor acupuncture modality would create a very complex model with over 15 variables. As described in the washout analysis, this will lead to overfitting of the model and cause it to be underpowered at 60 subjects. We could run a similar revised mixed liner model analysis substituting UU, UM or MU for MM, although this would be beyond the scope of Specific Aim 3.

Because of the exploratory nature of our analyses, no adjustment for multiple testing will be undertaken. Raw *P* values 0.05 will be regarded as statistically significant. Regardless, the multiple assessments inherent in the exploratory analysis will be discussed in future publications. Statistical analysis will be performed using SAS 9.1 (SAS Institute, Cary, NC).

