9. STATISTICAL CONSIDERATIONS

9.1. Sample Size Calculation

A mechanistic study of acupuncture, which examines its local, nerve-specific effects using Quantitative Sensory Testing (QST) and Nerve Conduction Studies (NCS) as outcome measures has not been attempted before. Therefore, we estimated acupuncture's effects based on larger studies drawn from the literature. Changes in acupuncture-associated sensation were derived from Lang et al (42) - an evaluation of manual and electroacupuncture- induced analgesia in the legs, using 24 healthy subjects, 12 men and 12 women, in a cross-over design. Effect sizes in Median nerve conduction velocity (NCV) were calculated as clinically relevant changes from the mean NCV reported by Kimura et. al (52) and Di Guglielmo et. al (53). Both studies were NCS characterizations specifically in CTS with 105 and 198 patients respectively and publicized in the AAEM summary statement on electrodiagnostic parameters in CTS (54).

QST testing from the Lang et al (42) acupuncture intervention was observed to be a significant predictor of Cold Detection Threshold (CDT), with a 0.2°C change ($-3.6 \pm 0.9^{\circ}\text{C}$ to $-3.4 \pm 0.4^{\circ}\text{C}$) seen in the low-frequency-acupuncture treated legs. As this study was conducted in healthy subjects, we expect to see a greater effect of acupuncture on patients with neuropathy, especially as the acupuncture will be administered locally, with greater potential to affect the underlying nerve. Sample size estimation assumed the variance of the change in QST outcomes due to local acupuncture delivery over the Median and Ulnar nerves will be comparable to the variance in QST observed by Lang after acupuncture in healthy nerves ($\sigma^2_{\text{CDT}} = 0.696 (^{\circ}\text{C})^2$). Under these assumptions, a minimum QST change of 0.35°C , considered reasonable as an on-treatment effect

size in CDT, would be observed as statistically significant at a significance level of $\alpha=0.05$ with 80% power with 20 subjects per arm.

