grouped by subject but the modality contrasts will be inter-subject and not require a serial correlation correction. With a significant difference observed by Lang et al with groups of n=6, the proposed sample size of 20 per intervention group should be more than sufficient to observe differences among the modalities, even without the explicit cross-over design. Please see statistical analysis plan for further details.

As the goal is to recruit 20 subjects per arm, for a total of 60 study completers, we anticipate the need to screen and enroll approximately 75 subjects, including with baseline nerve conduction studies to confirm the diagnosis of mild-moderate CTS and assure that the electrodiagnostic inclusion criteria for this study are met.

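### Aim 3 compares the three modalities on post-minus-pre change and does not name the outcome's own baseline as a covariate; naming it is a cheap, modest gain in precision (CDT power about 25% to 26–32%)

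*Combined protocol and SAP*

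**What the plan says.** Section 9.4 opens with "Primary statistical analysis for all 3 Specific Aims will use linear mixed-effect models" and defines the principal outcome as a difference: "Principal assessment will be on the change in outcomes resulting from acupuncture intervention, calculated as the difference in outcomes before and after treatment". Later it repeats that "the dependent outcomes of all models are the change in QST and NCS from baseline to post-acupuncture".

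For Aim 3, section 9.4 says the model will "focus on the MM factor from Specific Aims 1 and 2". This is the cell in which the median nerve is both treated and tested (MM), with modality added as a three-level factor. Section 9.3 describes Aim 3 more simply: acupuncture-induced changes "will be compared among the 3 groups (Post- minus Pre- changes), using ANOVA".

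The covariates named are week and, in an open list under the Aims 1 and 2 heading, age and gender: "Additional covariates known to be associated with QST and NCS outcomes such as age and gender will be corrected for as well". Section 9.4 does not say whether these carry over into the revised Aim 3 model. The outcome's own pre-treatment value is not named anywhere, although sections 5.2 and 6 have it measured at both visits.

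Section 9.1 accepts that "the modality contrasts will be inter-subject and not require a serial correlation correction".

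**The concern.** Restricting the model to MM leaves one change score per subject. The mixed model then reduces to an ordinary linear model on change across three randomised arms of 20. Subjects serve as their own controls for the median-versus-ulnar comparison, but that pairing does nothing for a contrast between modalities.

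In a randomised between-subject comparison, raw change fixes the coefficient on baseline at one. When pre and post values are imperfectly correlated, estimating that coefficient leaves less residual variance. The data needed are already collected.

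The open covariate list also leaves the choice to be made after the results are seen, in a plan with many outcomes and no multiplicity adjustment. What is at stake is precision and pre-specification, not validity.

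**Working it through.** **Inputs from section 9.1.** CDT effect 0.35°C, variance 0.696; NCV effect 3.7 m/s, SD 5.76 m/s (variance 33.2); 20 per arm; alpha 0.05; power 80%. The plan labels 0.696 as a variance of change: "Sample size estimation assumed the variance of the change in QST outcomes due to local acupuncture delivery over the Median and Ulnar nerves", taken from the cited healthy-volunteer study.

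**Assumptions not in the documents.** The 0.35°C and 3.7 m/s, given as on-treatment changes, are used as true differences between two modalities. Tests are two-sided. Pre and post SDs are equal. The pre/post correlation r is 0.5, 0.7 or 0.9. Other covariates explain no variance.

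**The plan's own figures.** For a within-arm change, n = (1.96 + 0.84)² × variance / effect².
- NCV: 7.85 × 33.2 / 3.7² = 19.03, so 20. This reproduces.
- CDT: 7.85 × 0.696 / 0.35² = 44.6, so 45. The stated 20 does not reproduce; with 20, power is about 47%.

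This is a separate matter, but it means the CDT inputs carry some doubt. The plan gives no power calculation for a difference between modalities.

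**Effect of the baseline term on CDT.** With equal SDs s, var(change) = 2s²(1−r) and the adjusted residual variance is s²(1−r²). The ratio is (1+r)/2. Power is from the noncentral t for 20 v 20, with 38 df for change and 37 df adjusted.

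| | Variance | Power at 0.35°C | Difference detectable with 80% power | n per arm for 80% |
|---|---|---|---|---|
| Change | 0.696 | 25.3% | 0.76°C | 91 |
| Adjusted, r = 0.5 | 0.522 | 32.0% | 0.66°C | 68 |
| Adjusted, r = 0.7 | 0.592 | 28.9% | 0.70°C | 77 |
| Adjusted, r = 0.9 | 0.661 | 26.4% | 0.74°C | 86 |

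As a check, the three-arm model with week, age and gender has 54 df, or 53 with baseline. Allowing also for chance imbalance in the covariate (variance factor 1 + 1/52), power goes from 25.6% to 31.9%, 28.8% or 26.3%. Break-even is at r = 0.961; above that the loss is at most 0.4 points.

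**NCV, 3.7 m/s.**

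| Reading of the NCV spread | r = 0.5 | r = 0.7 | r = 0.9 |
|---|---|---|---|
| 5.76 as single-time SD | 50.8% to 62.7% | 72.4% to 79.1% | 99.3% to 99.5% |
| 33.2 as variance of change | 50.8% to 62.7% | 50.8% to 57.3% | 50.8% to 52.8% |

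**The downside.** Half of each arm has the ulnar nerve treated first (section 4.4). For these subjects the MM baseline is the Week 2 value, taken after one session of the assigned modality. Suppose that session leaves a persistent, modality-specific shift c in the median nerve. Change cancels it. The adjusted model removes only the fraction r in the affected half, so the bias is about (1−r)c/2. For c = 0.35°C this is 0.09, 0.05 or 0.02°C at r = 0.5, 0.7 or 0.9.

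A simulation (20,000 runs, three arms of 20, week in the model) agreed:

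| Analysis | Bias with carry-over, no true effect (r = 0.5, 0.7, 0.9) | Null rejection | Power at 0.35°C, no carry-over |
|---|---|---|---|
| Change, no baseline term | 0.00 at every r | – | 26.0%, 26.0%, 25.4% |
| Same-session baseline | 0.088, 0.053, 0.019°C | 6.6%, 5.6%, 5.0% | 32.1%, 29.1%, 26.4% |
| Week 1 baseline, change as outcome | 0.00 | 4.8%, 5.0%, 4.9% | 27.0%, 26.5%, 25.4% |

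**The case against.** The strongest reply is that nothing is broken. Raw change is unbiased under randomisation, Aim 3 is a secondary aim of a pilot declared exploratory, and moving CDT power from 25% to at most 32% rescues nothing. All of that stands, and it is why this is an improvement and not an error.

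The post-randomisation baseline is a real cost, and the bias is largest where the gain is largest (r = 0.5). Section 5.2 says one session may alter the nerve, and section 5.1.3 separates the sessions because of residual effects. But section 5.2 speaks of each treated nerve respectively. Harm here needs a modality-specific effect of ulnar treatment on the median nerve that lasts a week. Section 3 leaves effects on a neighbouring nerve open; it does not assert them. Keeping raw change as primary, with adjustment as sensitivity, would also be defensible, provided the choice is written down beforehand.

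The size of the gain is uncertain:
- The only correlation cited (section 2.6, above 0.9) is not a pre/post-acupuncture correlation, but it makes the small-gain case realistic.
- The only before/after spread given for CDT (section 9.1, ±0.9 and ±0.4, healthy legs) is unequal. Read as SDs with change variance 0.696, it implies r = (0.81 + 0.16 − 0.696)/(2 × 0.9 × 0.4) = 0.38, residual SD 0.37 and adjusted power of about 83%.
- 0.696 also equals √((0.9² + 0.4²)/2), so it may be a pooled SD. Taken as the SD of change, power goes from 34% to 43%, 39% or 36%. Taken as a single-time SD, it goes from 34% to 43%, 52% to 58% and 93% to 94%.

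These readings change the absolute power, and the unequal-SD reading makes the gain much larger. None of them argues against naming the term. The open covariate list does permit a baseline term, which is a reason to settle it now.

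**Conclusion.** The point holds. The Aim 3 analysis is valid, but it leaves out a covariate that is already measured and would usually sharpen the modality contrasts. On the plan's labelled CDT variance, equal SDs and a 0.35°C difference between arms, the gain is about 7, 4 or 1 percentage points of power at r = 0.5, 0.7 or 0.9. For NCV it ranges from near zero to about 12 points. Adjustment does not make Aim 3 adequately powered for CDT on those inputs. The change should be made because it is nearly free and closes an open analytic choice. Confidence is medium: r is unknown and the CDT variance is of uncertain meaning.

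**What to change.** In sections 9.3 and 9.4, state one Aim 3 model for each outcome: MM change = modality + same-session median-nerve baseline of that outcome + week + age + gender.

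Add two sensitivity analyses, reported as estimates with 95% confidence intervals and not as further tests:
1. The same model without the baseline term.
2. The same model with the Week 1 pre-randomisation median baseline (section 3.4) as the covariate for all subjects, change remaining the outcome. This avoids the carry-over bias but gains 1 point of power or less.

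Say in the SAP that for ulnar-first subjects the same-session baseline follows one session of the assigned modality, and that the sensitivity analyses are there for that reason. Leave the four-level location model and the contrast between median-treated-and-tested and ulnar-treated-and-tested unchanged.

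The cost is SAP wording, one residual degree of freedom (54 to 53 with 60 subjects) and two extra model fits per outcome. No new data, visits or subjects are needed. The remaining price is the small, conditional bias sized above.
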